## **DETAILS OF PHASE 1: STANDARDISED PUBLIC HEALTH EVALUATION**

During Phase 1, data will be obtained from administrative records, health clinic staff, active TB patients and their household contacts.

### **STUDY POPULATION:**

#### **Participants:**

Potential participants are all index patients with newly diagnosed microbiologically confirmed active pulmonary TB (smear and/or culture positive active pulmonary TB) and their household contacts. Household contacts of all ages will be considered eligible. A household contact will be defined as someone who, in the preceding 3 months, slept in the same house at least one night per week, or spent more than 1 hour per day in the house for at least 5 days per week. The house will be defined as the dwelling, or buildings, which the family unit occupies and uses regularly.

#### **Selection of sites:**

Most of the involved countries, and investigators in this trial are participating in the ongoing pediatric and adult 4RIF v 9INH RCT for LTBI treatment trials. Research staff at these sites are well trained in clinical trials, enhancing feasibility of the proposed trial. In Vietnam, [name] and [name] of the University of Sydney have recently completed two large scale studies of contact investigations, and are initiating a randomized trial of LTBI treatment for contacts of patients with MDR-TB. Hence this group, and their Vietnamese collaborators have substantial experience in clinical research, particularly in contact investigations.

**Table 1: Anticipated number of active TB cases, and their house-hold contacts at the sites**

Country	Number of Patients with PTB		Close Contacts		Randomization Units**
	Annually	In 18 months	Identified #	With LTBI ## (TST pos.)	
*Canada	250	375	1575	450	4
*Benin	500	750	3150	1600	2
*Ghana	300	450	1900	975	2
*Indonesia	300	450	1900	975	8
Vietnam	300	450	1900	975	8
Total	1650	2475	10,425	4975	24

\* RCT sites that are participating in the 4RIF/9INH trial and will participate in this study

\*\* Randomization units - These are health facility-based units for which all of the interventions can be implemented, independent of other units in the same country.

# Estimated based on 4.2 contacts identified per active TB case - from systematic review 

## Estimated based on prevalence of LTBI among contacts screened: of 51.5% in LMIC , and 28.1% in Canada .

We anticipate that our study objectives can be met with this number of sites or clinics (which will be the units of randomization) in each country. This number of sites is considered optimal for several reasons: i) ensures variation in clinic staff, setting and population; ii) avoids experience overly skewed by one or two high performing (or poorly performing) clinics;

Each site should have an adequate number of contacts – but this may be unknown before Phase 1 begins. Hence each unit of randomization (ie each clinic), should have diagnosed an annual average of at least 40 patients with active pulmonary TB in each of the preceding 3 years - in order to have enough contacts to study (from prior systematic reviews, on average 4.2 household contacts are identified per active PTB patient in LMIC).

A narrative description of the functioning of the TB programme, particularly contact investigation, at each site will be written by the research staff, with the input of a member of the site's administrative staff. This narrative will also describe how active TB is diagnosed and treated, how LTBI prophylaxis and contacts are presently managed, plus the diagnostic capacity of the facility (eg whether Chest X-rays are done on site).

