**Indonesia:** In Indonesia, the National TB Programme (NTP) has recognized the high risk of disease in contacts and adopted symptom screening of contacts, but this is rarely implemented, and is not recorded nor reported. Bandung city in West Java, Indonesia has a population of approximately 2.5 million. The greater Bandung area, however, has a population of over 7 million. The incidence of new smear positive TB is approximately 100 per 100,000 population for a total case load of approximately 2000 new cases each year. Both the city and the area is served by a network of community based primary care clinics. The adult and pediatric trials comparing 4RIF and 9INH recruited patients from community clinics in the central Bandung area, in conjunction with a clinic at the University of Padjadjaran. We propose to conduct the study in 8 of these community clinics - where the current LTBI trial was well received, and well executed.

**Vietnam:** At the Vietnam site, household contacts are identified by clinical officers working at District Tuberculosis Units (DTU). The clinical officers interview newly diagnosed patients with active TB, and make a list of household contacts that are eligible for screening. These contacts attend the DTU for clinical assessment and chest X-ray. TST is not routinely performed. Despite national policies recommending 6INH for contacts who are children or with known HIV infection, few are treated.

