#### **Sample size considerations:**

As seen in Table 1 above (Study population), we estimate that during the 18 months of the study, 2475 active TB cases will be diagnosed at the participating sites, and 10,425 contacts will be identified, of whom 4975 will be diagnosed with LTBI. We wish to detect a 15% increase in the proportion of contacts that initiate therapy, with a level of statistical significance of 0.05 (alpha error). The intra-class correlation coefficient (ICC) which describes the inter-cluster heterogeneity, (or analogously the correlation amongst subjects in the same cluster) has less effect, but to be conservative we will assume this to be 0.05 to 0.1– which is high. In data from the 9INH vs 4RIF trial (comprising 6031 adults treated for latent TB in 12 centres), the ICC for the centre effect was low – just 0.01-0.02, depending on the method used to estimate it, for treatment completion. We will have 24 clusters in 5 countries. Our power calculations are based on the number of close contacts identified per randomization unit (from Table 1).

**Table 2: Detectable differences with all sites in all countries** (alpha=.05, and Power = 80%)

Proportion starting LTBI therapy in Control Arms	N Contacts per clinic	Design Effect	Total sample size per arm	Intra-Class Correlation	Detectable difference
0.10	100	2.0	1222	0.01	0.05
0.10	100	6.0	1214	0.05	0.10
0.10	100	10.9	1199	0.10	0.14
0.30	100	2.0	1236	0.01	0.08
0.30	100	6.0	1261	0.05	0.13
0.30	100	10.9	1221	0.10	0.18

Therefore, given 24 clusters in 5 countries, with at least 100 contacts per site every 6 months (based on minimum 40 active cases every year, and estimated 4.2 contacts per index case), and assuming that at baseline only 10% of contacts are started on Latent TB therapy, plus an ICC of 5%, we would have 80% power to detect a 10% increase in proportion of contacts starting therapy. If the number of contacts per site is higher this will actually have a modest effect on the detectable difference. If the proportion starting therapy is much higher (30%), then the detectable difference would be near 13%.

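### The minimum of 40 pulmonary TB patients a year per clinic, on which the power statement rests, is incompatible with Table 1, where Indonesia and Vietnam average 37.5 per clinic

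*Protocol*

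**What the plan says.** The text under Table 1 (Selection of sites) says that "each unit of randomization (ie each clinic), should have diagnosed an annual average of at least 40 patients with active pulmonary TB". It applies this to the 3 years before the trial, so that there are enough contacts to study.

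Table 1 gives, for each country, annual cases, cases in 18 months, contacts identified, contacts with LTBI, and randomization units. The two rows at issue read "Indonesia 300 450 1900 975 8" and "Vietnam 300 450 1900 975 8", and the last row reads "Total 1650 2475 10,425 4975 24".

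Other sections confirm the unit counts. For Indonesia, Specific Sites says "We propose to conduct the study in 8 of these community clinics". For Vietnam, the section on selecting Phase 2 solutions describes two provinces with four health centres each.

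Sample size considerations claims 80% power to detect a rise from 10% to 20% with 24 clusters and an ICC of 0.05. It assumes at least 100 contacts per site every 6 months, "based on minimum 40 active cases every year" and 4.2 contacts per index case. The Phase 2 paragraph on recruitment rate says the contact estimates come from cases seen annually at these sites over the past 3 to 5 years, with no major change expected.

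**The concern.** One figure, 40 cases a year, is used both as an entry rule for clinics and as an input to the power statement. Table 1 contradicts it for the two countries that supply 16 of the 24 clusters. Whoever confirms the sites must depart from either the rule or the list, and the protocol does not say which.

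If the rule is applied to the listed clinics, clusters are lost, and with this ICC the number of clusters matters more to power than the number of contacts per clinic. If the rule is waived, the minimum quoted in the sample size section is false. The choice also decides which clinics may be randomized, so it should be settled before allocation.

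**Working it through.** **Inputs.** Annual cases and units from Table 1: Canada 250 over 4, Benin 500 over 2, Ghana 300 over 2, Indonesia 300 over 8, Vietnam 300 over 8. Minimum of 40 cases a year, from the text under Table 1. From Sample size considerations: 4.2 contacts per case, 24 clusters, 100 contacts per clinic, ICC 0.05, alpha 0.05, power 80%. The section does not say whether alpha is one- or two-sided. Two-sided is assumed here, with 12 clusters per arm.

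**Step 1: reproduce the plan's figure (10% vs 20%, ICC 0.05).**
- Unclustered n per arm = [1.96 × √(2 × 0.15 × 0.85) + 0.842 × √(0.10 × 0.90 + 0.20 × 0.80)]² / 0.10² ≈ 199.
- Design effect = 1 + 99 × 0.05 = 5.95 (the table shows 6.0).
- 199 × 5.95 ≈ 1184 per arm. Table 2 states 1214, so this agrees to within 3%.
- With 12 × 100 per arm, the effective n is 1200 / 5.95 ≈ 201.7 and power is 80.5%. The stated 80% is reproduced.

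**Step 2: test the rule against Table 1.**
- Mean cases per clinic a year: Canada 62.5, Benin 250, Ghana 150, Indonesia 300/8 = 37.5, Vietnam 37.5.
- Needed for eight clinics at 40: 8 × 40 = 320, which exceeds 300. However the cases are spread, at least one clinic in each country falls short.
- Most that can qualify: 300/40 = 7.5, so 7 per country.
- Ceiling on qualifying clusters: 4 + 2 + 2 + 7 + 7 = 22.

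**Step 3: rule enforced, no substitution.** With 22 clusters (11 per arm) of 100 contacts, the effective n is 1100 / 5.95 ≈ 184.9 per arm. Power for 10% vs 20% is 77.0%, and the difference detectable with 80% power is about 10.5 points. This is a best case, because fewer than 7 clinics per country may pass.

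**Step 4: rule waived, all 24 kept.** Contacts per clinic in 6 months = annual cases × 4.2 / 2.
- At 37.5 cases: 78.75 contacts. Design effect = 1 + 77.75 × 0.05 = 4.8875. If all 24 clinics were this size, effective n = 12 × 78.75 / 4.8875 ≈ 193.3 per arm and power is 78.9%.
- At exactly 40 cases: 84 contacts, not at least 100, and power is 79.3%. Reaching 100 contacts needs 100 / 2.1 ≈ 48 cases a year.
- With Table 1's own mean sizes (131.25, 525, 315, and 78.75 in both Indonesia and Vietnam), summing m / (1 + (m − 1) × 0.05) over half the clinics of each country gives 2 × 17.47 + 19.30 + 18.86 + 8 × 16.11 ≈ 202 per arm. Power is about 80.6%. This assumes efficient (exchangeable) weighting.

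**Step 5: the 15-point increase also named in the sample size section.** From 10% at ICC 0.05 and 100 contacts per clinic, power is about 98% with 24 clusters and 97% with 22. From 30% it is about 88% and 85%.

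**The case against.** The strongest reply is that this is a shortfall of about 6% (37.5 against 40) between a loosely worded criterion and a planning table. The rule says clinics should meet 40, Table 1 is headed "Anticipated number of active TB cases, and their house-hold contacts at the sites", and three of its five countries carry the same round figure of 300. The protocol gives no clinic-level counts. For Indonesia it describes a network of clinics with about 2000 new smear-positive cases a year, so eight clinics at 40 would need 320/2000 = 16% of that load. Clinics that meet the rule could simply be chosen.

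Much of this stands. Substitution is plausible in Indonesia, so lost clusters are a consequence only if the rule is enforced on a fixed list. No comparable caseload is given for Vietnam. The rounding argument helps little: even if 300 were rounded to the nearest 50 (an assumption), the true total would be below 325, a mean of at most about 40.6. All eight clinics would then have to be almost the same size. Nor can the figures be set aside as mere forecasts, since the protocol bases its contact estimates on past annual case numbers at these sites.

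A reader might go further and infer that only 20 clusters remain, on the ground that each country needs an even number of clinics. The documents do not support this. Study design and Randomization ask for balance in participants or contacts, not in numbers of clinics, so a 4:3 split is allowed. A reader might also infer that the trial is seriously underpowered. Steps 4 and 5 show otherwise for the entry rule. Weighting all contacts equally, with Table 1's sizes, would lower power to about 59%, but that comes from the very large clinics in Benin and Ghana, not from the minimum of 40.

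**Conclusion.** The contradiction holds. A minimum of 40 cases per clinic, 8 units in each of Indonesia and Vietnam, and 300 cases a year in each country cannot all be true. Enforced on the listed clinics without substitution, the rule leaves a ceiling of 22 clusters and at most about 77% power for 10% versus 20%. With all 24 clinics kept, the loss of power is small (about 79% to 80%), but both the stated minimum of 40 and the figure of at least 100 contacts per site are unsupported.

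This is a wrong figure in an eligibility rule and in the power statement built on it, not a threat to the trial's main aim. The power figures assume a two-sided 5% test, a normal approximation with pooled variance, equal numbers of clusters per arm and an ICC of 0.05. The Table 1 counts are taken as representing the 3 years to which the rule refers.

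**What to change.** Before randomization, bring Table 1, the entry rule beneath it and Sample size considerations into agreement in one of two ways.

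- Lower the stated minimum to a figure that all 16 Indonesian and Vietnamese clinics meet. Use it in the power statement and Table 2, with the contacts per 6 months that follow from it (cases × 4.2 / 2).
- Keep 40, confirm from clinic-level counts which units meet it, substitute where possible, and restate the case counts or the number of units. Recalculate Table 2 with the resulting number of clusters and with 84 contacts per site as the minimum, in place of 100.

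Either way the cost is protocol wording and one recalculated table. No extra enrolment is needed to correct the text, though the stated minimum or the stated power becomes slightly less favourable.

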**Planned recruitment rate:**

The number of participants needed for Phase 1 is small, relative to the large numbers of patients with disease, and their contacts seen at each site. So we do not anticipate problems in recruitment of adequate numbers in Phase 1.

**Specific Sites:**

**Montreal:** The Montreal Chest Institute houses the largest adult TB clinic in Montreal, and is now adjacent to the TB clinic of the Montreal Children's Hospital. Household contacts are identified by the nurses of the TB clinic, and the Montreal public health unit, during interviews with patients who are newly diagnosed with active PTB. Home visits are made for some newly diagnosed TB patients. TST administration and reading is performed at the TB clinics or at community clinics; those with positive TST are referred for medical evaluation to the hospital-based TB clinics. There is no follow-up for contacts who fail to complete TST, or to present for evaluation. LTBI therapy is individualized.

**Vancouver:** In Vancouver, household contacts are identified by the public health nurses during an interview with each patient with newly diagnosed active PTB. Household contacts undergo symptom inquiry, TST, and reading at their local public health unit or during a home visit. If symptomatic or a positive TST, the contact is referred to the TB Clinic, for evaluation. The Vancouver BCCDC TB Clinic works with the Vancouver Coastal Health Authority, and is involved in the 4RIF vs 9INH trial. The New Westminster TB Clinic serves the Fraser Health Authority, has separate staffing, and will be the second site.

**Edmonton:** In Edmonton, newly diagnosed patients with active pulmonary TB are assigned a public health nurse who is based at the Edmonton Public Health TB Clinic, the proposed trial site. The nurse interviews the patient and family in the clinic, or if this cannot be arranged, the nurse will make a home visit. All screening investigations and clinical evaluations are performed at the TB clinic. Identified contacts that do not come to the clinic for assessment are telephoned (twice) by the clinic nurse, and if unsuccessful, a letter is sent. This clinic will be matched with the Calgary site for randomization.

**Calgary:** In Calgary, all patients newly diagnosed with active PTB are assigned a public health nurse who is based at the Calgary Public Health TB Clinic. This nurse interviews the family in the clinic, or if this cannot be arranged, the nurse will make a home visit. Identified contacts that do not come to clinic are contacted via telephone twice and if unsuccessful, a letter is sent on two occasions. Contacts that live in the city of Calgary are referred to the Foothills hospital TB clinic for evaluation. If they do not come the public health nurse will call them twice. If LTBI is diagnosed, LTBI therapy is individualized. Individuals who drop out during LTBI therapy are called by clinic staff.

**Benin:** The Benin NTP policy is to ask all newly diagnosed active pulmonary TB cases to bring all children aged under 5 living in the same household to the nearest TB treatment facility for evaluation. The patient is also asked to advise all symptomatic household contacts to visit diagnostic centres for evaluation. Home visits are not done to identify or screen contacts. The adult and pediatric 4RIF vs 9INH trials are being conducted at the Centre National de Pneumo-Phthisiologie (CNPP) in Cotonou. The randomization units for the proposed trial will be two independently staffed treatment centres in Cotonou – the CNPP, and the Centre de Akron a Portonovo.

**Ghana:** In Kumasi, Ghana, all patients newly diagnosed with active pulmonary TB are interviewed, and screened for symptoms of active PTB. Contacts that do not have symptoms are not assessed further except for children under the age of 5 and known HIV infected persons – who are referred to the hospital TB clinic, where they receive 6 months INH. Individuals who drop out during LTBI therapy are contacted by telephone.

**Indonesia:** In Indonesia, the National TB Programme (NTP) has recognized the high risk of disease in contacts and adopted symptom screening of contacts, but this is rarely implemented, and is not recorded nor reported. Bandung city in West Java, Indonesia has a population of approximately 2.5 million. The greater Bandung area, however, has a population of over 7 million. The incidence of new smear positive TB is approximately 100 per 100,000 population for a total case load of approximately 2000 new cases each year. Both the city and the area is served by a network of community based primary care clinics. The adult and pediatric trials comparing 4RIF and 9INH recruited patients from community clinics in the central Bandung area, in conjunction with a clinic at the University of Padjadjaran. We propose to conduct the study in 8 of these community clinics - where the current LTBI trial was well received, and well executed.

**Vietnam:** At the Vietnam site, household contacts are identified by clinical officers working at District Tuberculosis Units (DTU). The clinical officers interview newly diagnosed patients with active TB, and make a list of household contacts that are eligible for screening. These contacts attend the DTU for clinical assessment and chest X-ray. TST is not routinely performed. Despite national policies recommending 6INH for contacts who are children or with known HIV infection, few are treated.

## **DATA GATHERING:**

### **Study Outcomes:**

Based on the primary study objective, the key data to be collected prospectively after the trial begins is the number of patients diagnosed with microbiologically confirmed Pulmonary TB (index cases) (also will collect number of not confirmed pulmonary and not pulmonary), the number of identified household contacts of these index cases with confirmed pulmonary TB, and the number of household contacts who started LTBI therapy. Note that the number who actually complete therapy is not required as this is a secondary outcome that occurs later and data will be collected retrospectively. The primary study outcomes of number of index cases, number of household contacts identified and the number of household contacts starting LTBI therapy must be measured every month at all health facilities (Intervention and Control) throughout the trial. Outcomes will be recorded using a standardized form. More detail on data sources and how to ascertain study outcomes is provided below.

### **Ascertainment of study outcomes - at all sites:**

Ultimately, in the intervention sites we will be able to use the newly developed and introduced Contact Management Registries (see below) to extract all necessary information and outcomes – including number of pulmonary TB cases (Index cases), number of contacts identified, and number who initiate LTBI therapy. However, these detailed contact registries are considered an integral part of the public health intervention, since considerable training in recording and reporting as well as the procedures of contact management will be needed for these to be completed accurately and completely. Introduction of these registries at control sites would be difficult without extensive training; if such training was given at the control sites, this would constitute a partial intervention, and reduce potential differences between intervention and control sites.

Hence recording of outcomes at control and intervention sites must rely on simple measures that can be implemented with minimal training, prior to the start of the trial at all sites. It is important that the procedures to ascertain (measure) these outcomes be established at the beginning of Phase 1, and continue **unchanged** at all health facilities (both intervention and control facilities) through-out the 18 months of the study.

Identification of contacts may not be performed, or not clearly recorded at all health facilities – especially the control facilities. This is why we must carefully document the number of index patients with active pulmonary TB diagnosed at each site. When the study is completed, the coordinating centre may use the number of index cases to estimate the number of household contacts that likely could have been identified (see Analysis section) Data sources will vary by site, depending what methods of documentation are already being used. We will collect information on the number of newly diagnosed index cases from lab or other sources that report active cases. The number of household contacts indentified will come from different sources depending on what is available the site. Finally, we will estimate the number of contacts who start LTBI treatment from hospital and or clinic records using a standard data collection form in all sites. The number of contacts completing LTBI therapy will be estimated retrospectively from clinic records.

